### **2.2 Secondary Outcomes**

#### **1. 28-Day Organ Support Free Days**

Organ support free days is defined as a patient being alive and without assisted breathing, new renal replacement therapy, or vasopressors (beyond 48 hours). Patients will be followed for use of organ support to death, hospital discharge or study day 27, whichever comes first. Any day that a patient is alive and without organ support will represent days alive and free of organ support. Since there will be a bias in the protocols to place patients on vasopressors in the restrictive group, vasopressor use prior to 48 hours will be excluded from this calculation for both groups.

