7.3 Other Assessments and Data Collection

1. Vasopressor use over the hospitalization
2. Assisted ventilation over the hospitalization
3. New renal replacement therapy over the hospitalization
4. Daily fluid administration for the first 7 days
5. Daily fluid outputs (truncated for death or ICU discharge) for the first 7 days
6. Diuretic administration over the first 7 days
7. Clinical laboratory testing results during the first 72 hours post randomization
8. Results of microbiologic testing from samples taken over the first 72 hours after randomization
9. SOFA at hours 0 and 72

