**2. 28-day Ventilator Free Days (VFDs)**

VFDs depend on both duration of ventilation and mortality through study day 28. In participants who survive 28 days, VFD is defined as 28 minus duration of ventilation. Duration of ventilation is counted from the first study day of assisted breathing through the last day of assisted breathing provided the last day is prior to day 28. Otherwise, it is counted from the first study day of assisted breathing through day 28. For participants discharged with assisted ventilation (e.g., to LTAC facility) prior to day 28, a phone call will be required to assess ventilator and vital status at day 28. Participants discharged prior to day 28 on unassisted breathing will be assumed to remain on unassisted breathing through day 28. Isolated periods of ventilation briefer than 24 hours for surgical procedures and ventilation solely for sleep disordered breathing do not count towards duration of ventilation. In participants who never require assisted breathing, duration of ventilation is zero. Participants who do not survive 28 days will be assigned zero VFD. VFD is undefined in participants with chronic/home mechanical ventilation (except solely for sleep disordered breathing) and they will be excluded from this analysis.

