**3. 28-day Renal Replacement Therapy Free Days**

Renal replacement free days to day 28 are defined as the number of calendar days between randomization and 28 days later that the patient is alive and without renal replacement therapy. We also follow the “last off” method. Patients who died prior to day 28 and those who receive renal replacement therapy for the entire first 28 days are assigned zero renal replacement free days.

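### Organ-support follow-up stops at hospital discharge and only ventilation has a post-discharge rule, so a patient discharged on new dialysis can be credited with support-free days

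*SAP*

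**What the plan says.** **Composite (SAP 2.2 item 1; same wording in Protocol 3.6.2 item 1).** The follow-up rule is "Patients will be followed for use of organ support to death, hospital discharge or study day 27, whichever comes first". The counting rule is "Any day that a patient is alive and without organ support will represent days alive and free of organ support". Nothing is said about the days between discharge and day 27.

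**Ventilator free days (SAP 2.2 item 2).** Both discharge states are covered. For those still on support, "For participants discharged with assisted ventilation (e.g., to LTAC facility) prior to day 28, a phone call will be required". For those off it, "Participants discharged prior to day 28 on unassisted breathing will be assumed to remain on unassisted breathing through day 28".

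**Renal replacement free days (SAP 2.2 item 3).** The outcome is "the number of calendar days between randomization and 28 days later that the patient is alive and without renal replacement therapy", counted by a last-off method that is not defined further. Apart from deaths, "those who receive renal replacement therapy for the entire first 28 days are assigned zero renal replacement free days". There is no cut at discharge and no rule for patients discharged on or off dialysis.

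**Data collection.** Protocol 7.3 lists "New renal replacement therapy over the hospitalization". Protocol Appendix F has one row covering ventilator, vasopressor and renal replacement use, which appears to be marked at day 28. The table is damaged in the text available, so the column is probable rather than certain.

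**Missing data (SAP section 5).** There is no imputation except for selected derived variables, with SOFA given as the example.

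**The concern.** The composite and the renal outcome need a value for every day to day 27 or 28, but the stated observation of dialysis ends at discharge. If scoring uses only what was observed, the last recorded dialysis day is an in-hospital day and the days after it look free. Continued dialysis dependence would then score like renal recovery. The zero score for therapy throughout the 28 days cannot be reached from in-hospital records by someone who left on day 10.

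The ventilation item shows that the authors saw this problem for one organ and dealt with it. For dialysis, two programmers could score the same patient as free, on support or missing. The trial is not blinded, so that choice should be fixed in advance.

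The composite is not a minor outcome here. Protocol 9.2 presents it as one whose result could change practice. Protocol 3.3 also gives reasons to expect a renal effect (tissue oedema affecting the kidney, and less acute kidney injury with restriction in a small trial), so the two arms could differ in how many patients leave on dialysis.

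**Working it through.** **1. The plan's own figure for this outcome.** Protocol 9.2 uses SD 12, two-sided alpha 0.05 and 90% power. Total n = 2 × [2 × (1.960 + 1.282)² × 12² / d²], rounded up per arm.

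| Difference d (days) | Computed total | Protocol total |
|---|---|---|
| 4 | 380 | 382 |
| 3 | 674 | 676 |
| 2 | 1514 | 1516 |

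All agree within 2 patients, so the same SD and alpha are used below.

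**2. Precision at full enrolment.** With 2320 randomized 1:1, there are 1160 per arm. SE of the difference = 12 × √(2/1160) = 0.498 days. The smallest significant difference is 1.96 × 0.498 = 0.98 days. The difference detectable with 90% power is 3.242 × 0.498 = 1.62 days.

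**3. Credit per affected patient.** Randomization is study day 0 (Protocol 1.2), so the composite runs over days 0 to 27. A patient discharged on day D and still on dialysis to day 27 gains 27 − D days if post-discharge days are counted as free: 20, 17, 13 or 7 days for D = 7, 10, 14 or 20.

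**4. Effect on one arm's mean.** The documents give neither the share q discharged alive on new dialysis nor the day D. Both are assumptions here: q from 0.5% to 3%, D from 10 to 20. Rise in the mean = q × (27 − D).
- Lowest: 0.005 × 7 = 0.035 days
- Highest: 0.03 × 17 = 0.51 days

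**5. Effect on the arm difference.** Only an imbalance matters. With q differing by 0.5 to 2 points and the same D in both arms:
- Lowest: 0.005 × 7 = 0.035 days, about 1% of the 3 days that Protocol 9.2 calls clinically significant
- Highest: 0.02 × 17 = 0.34 days, about 11% of 3 days

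If q and D are the same in both arms, both means rise equally and the difference is unchanged.

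**6. Effect on power, if the shift runs against the true effect.** Power = Φ(effect/SE − 1.96).
- True difference 3 days, shift 0.34: 2.66/0.498 − 1.96 = 3.38, so power stays above 0.999.
- True difference 1 day, no shift: 0.52.
- True difference 1 day, shift 0.035: 0.49.
- True difference 1 day, shift 0.34: 0.26.

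**7. The texts side by side.** The discharge cut-off stands in item 1. Item 3 runs to 28 days without it. Protocol 7.3 collects in-hospital use only. Appendix F appears to ask for use at day 28. If that row means contact after discharge, it conflicts with item 1 and Protocol 7.3. If it means a day-28 summary of hospital use, nothing fills the gap. On either reading, no scoring rule refers to it.

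**The case against.** A reader might infer that the plan scores dialysis-dependent patients as recovered. The documents do not say so. Item 1 credits only days alive and without support, and a day on dialysis at home or in another facility fails that test. The discharge cut-off is in item 1, not item 3. To reach the same result in item 3, one must assume that only in-hospital data feed it and that the last recorded session counts as last off. Item 2 follows patients past discharge, so item 1's sentence evidently does not govern every component. Item 3's 28-day window is also a natural user of the Appendix F check.

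The effect is also assumed and small. A 1-point imbalance moves the difference by 0.07 to 0.17 days for D from 20 to 10, against an SE of about 0.5. These patients also remain visible in the separate outcome of starting renal replacement by day 28.

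Most of this stands, and it limits the point to what can happen under the plan's silence. It does not remove the point. A definition that excludes dialysis days helps only if those days are observed. Item 1 and Protocol 7.3 stop observation at discharge, and nothing ties the Appendix F row to a score.

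**Conclusion.** The point holds as a gap and an internal conflict. As written, a patient discharged on new dialysis can be credited with support-free days in the composite, and in renal replacement free days if only in-hospital data are used. The documents do not establish that such credit is the intended rule.

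Under the assumed shares and discharge days, one arm's mean is too high by about 0.04 to 0.5 days, and the arm difference shifts by about 0.04 to 0.34 days. The shift is toward no difference if the arm with more dialysis-dependent discharges is otherwise the worse one, and away from it if that arm is otherwise the better one. It is immaterial for a true 3-day effect but could matter for an effect near 1 day. Only secondary outcomes are touched. The primary outcome, the 2320 total and the Protocol 9.2 table do not change. It should be corrected because the remedy is cheap and the protocol gives this outcome weight.

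**What to change.** Reconcile SAP 2.2 items 1 and 3, Protocol 3.6.2, Protocol 7.3 and Protocol Appendix F by extending the item 2 ventilation rule to new renal replacement therapy in items 1 and 3:

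- Patients discharged off new renal replacement therapy are assumed to stay off through day 28.
- For patients discharged on it, day-28 status and any stop date are obtained at the scheduled day-28 check and used in scoring.
- If no stop date is obtained, the patient is scored as on support through day 28. A sensitivity analysis credits those days instead.

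In the same edit, add the word *new* to SAP 2.2 item 3, to match SAP 1.9 and Protocol 3.6.2 item 3.

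The cost is a few sentences and one added question for a small number of patients. The downside is that the default may under-credit patients who came off dialysis after discharge without a recorded date. The sensitivity analysis shows how much that matters. This is an outcome-scoring rule and changes no clinical care.

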**2. 28-day Ventilator Free Days (VFDs)**

VFDs depend on both duration of ventilation and mortality through study day 28. In participants who survive 28 days, VFD is defined as 28 minus duration of ventilation. Duration of ventilation is counted from the first study day of assisted breathing through the last day of assisted breathing provided the last day is prior to day 28. Otherwise, it is counted from the first study day of assisted breathing through day 28. For participants discharged with assisted ventilation (e.g., to LTAC facility) prior to day 28, a phone call will be required to assess ventilator and vital status at day 28. Participants discharged prior to day 28 on unassisted breathing will be assumed to remain on unassisted breathing through day 28. Isolated periods of ventilation briefer than 24 hours for surgical procedures and ventilation solely for sleep disordered breathing do not count towards duration of ventilation. In participants who never require assisted breathing, duration of ventilation is zero. Participants who do not survive 28 days will be assigned zero VFD. VFD is undefined in participants with chronic/home mechanical ventilation (except solely for sleep disordered breathing) and they will be excluded from this analysis.

**3. 28-day Renal Replacement Therapy Free Days**

Renal replacement free days to day 28 are defined as the number of calendar days between randomization and 28 days later that the patient is alive and without renal replacement therapy. We also follow the “last off” method. Patients who died prior to day 28 and those who receive renal replacement therapy for the entire first 28 days are assigned zero renal replacement free days.

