3.6.2 Secondary Outcomes

1. 28-Day Organ Support Free Days

Organ support free days is defined as a patient being alive and without assisted breathing, new renal replacement therapy, or vasopressors (beyond 48 hours). Patients will be followed for use of organ support to death, hospital discharge or study day 27, whichever comes first. Any day that a patient is alive and without organ support will represent days alive and free of organ support. Since there will be a bias in the protocols to place patients on vasopressors in the restrictive group, vasopressor use prior to 48 hours will be excluded from this calculation for both groups.

2. 28-day Ventilator Free Days (VFDs)

VFDs depend on both duration of ventilation and mortality through study day 28. In participants who survive 28 days, VFD is defined as 28 minus duration of ventilation. Duration of ventilation is counted from the first study day of assisted breathing through the last day of assisted breathing provided the last day is prior to day 28. Otherwise, it is counted from the first study day of assisted breathing through day 28. For participants discharged with assisted ventilation (e.g., to LTAC facility) prior to day 28, a phone call will be required to assess ventilator and vital status at day 28. Participants discharged prior to day 28 on unassisted breathing will be assumed to remain on unassisted breathing through day 28. Isolated periods of ventilation briefer than 24 hours for surgical procedures and ventilation solely for sleep disordered breathing do not count towards duration of ventilation. In participants who never require assisted breathing, duration of ventilation is zero. Participants who do not survive 28 days will be assigned zero VFD. VFD is undefined in participants with chronic/home mechanical ventilation (except solely for sleep disordered breathing) and they will be excluded from this analysis.

3. 28-day Renal Replacement Therapy Free Days

Renal replacement free days to day 28 are defined as the number of calendar days between randomization and 28 days later that the patient is alive and without new renal replacement therapy. We also follow the “last off” method. Patients who died prior to day 28 and those who receive renal replacement therapy for the entire first 28 days are assigned zero renal replacement free days.

4. 28-day Vasopressor Free Days

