## 1.9 Secondary Endpoints

1. 28-day organ support free days (alive and without mechanical ventilation, new renal replacement or vasopressors; vasopressors prior to 48 hours excluded)
2. 28-day ventilator free days
3. 28-day renal replacement free days (new renal replacement therapy)
4. 28-day vasopressor free days (vasopressors prior to 48 hours excluded)
5. 28-day ICU free days
6. 28-day hospital free days to discharge home
7. Initiation of mechanical ventilation to day 28
8. Initiation of renal replacement therapy to day 28
9. Change in creatinine-based KDIGO stage between baseline and 72 hours
10. Change in SOFA score between baseline and 72 hours
11. 90-day all-cause mortality
12. Development of ARDS within 7 days
13. New onset atrial or ventricular arrhythmia to day 28
14. Additional secondary safety endpoints:
  - a. New intubation through day seven
  - b. New mechanical ventilation through day seven
  - c. Ventricular arrhythmias in first 24 hours
  - d. New renal replacement therapy through day seven
  - e. New ARDS through day seven
  - f. ICU admission through day seven
  - g. Central venous line insertion through day three
  - h. Vasopressor infusion through peripheral venous catheter
  - i. Line complications of central venous catheter placement
  - j. Line complications
  - k. More than three line complications among patients with a line complication
  - l. Site extravasation to day 28 from peripheral venous catheter infusion
  - m. New ventilation and oxygen use in first 24 hours
  - n. Adverse events

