**8. Initiation of renal replacement to day 28**

Patients who receive (new) renal replacement therapy through day 28 will meet this endpoint. Patients with chronic renal replacement therapy initiated prior to the current sepsis illness will not be eligible to meet this endpoint.

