### 3. Subgroups for Secondary Analysis

1. Patients receiving chronic dialysis
2. Patients with history of chronic heart failure (as documented in past medical history)
3. Patients with qualifying SBP < 90 mmHG versus 90-100 mmHG at randomization

4. Patients age > 65 years of age
5. Patients with a clinically confirmed infection as a cause of hypotension at study enrollment (as assessed by the investigator using records available throughout hospitalization)
6. Patients with pneumonia as the etiology of sepsis
7. Stratification by SOFA score quartiles on enrollment
8. Patients enrolled in the ED (vs. wards or ICU)
9. Use of cardiac ultrasound or other hemodynamic monitoring techniques (yes or no; defined in Section 5.3)
10. Patient with a history of hypertension (as documented in past medical history or by the prescription of chronic medications)
11. Patients enrolled prior to and following the protocol change regarding required or optional use of the second liter of fluid infusion in the liberal treatment arm.

As per NIH guidelines we will also do secondary analysis by sex, ethnicity, and race.

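### SAP section 2.2 drops the word *new* from renal-replacement-free days, contradicting its own endpoint list and the protocol, and no rule covers patients on chronic dialysis

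*SAP*

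**What the plan says.** The SAP describes this endpoint twice. Its list in section 1.9, item 3, limits it to new renal replacement therapy. Its working definition in section 2.2, item 3, counts calendar days "that the patient is alive and without renal replacement therapy", with no such limit. That definition then applies the last-off method and gives zero to deaths before day 28; "those who receive renal replacement therapy for the entire first 28 days are assigned zero renal replacement free days".

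Protocol section 3.6.2, item 3, has otherwise the same sentence, but counts days "that the patient is alive and without new renal replacement therapy". Protocol section 2.9, item 3, also says new therapy.

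No exclusion criterion in either document removes patients on chronic dialysis, and the first subgroup in SAP section 3 is "Patients receiving chronic dialysis". For item 8, initiation of renal replacement, the SAP has a rule: "Patients with chronic renal replacement therapy initiated prior to the current sepsis illness will not be eligible to meet this endpoint". Item 3 has no equivalent sentence in either document.

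**The concern.** A programmer would code the endpoint from the detailed definition, and that is the one place where the qualifier is missing. A patient who arrived already on dialysis and continues it would then be scored as having lost those days to organ failure, close to the score given to a death. This happens in both arms and says almost nothing about the fluid strategy. The scores pull the two means together and widen the spread, and SAP section 5 then compares the means with a t-test.

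Section 5 also adds treatment-by-subgroup interaction terms for the secondary outcomes. In the chronic dialysis subgroup the score would hardly vary among survivors followed to day 28, so the interaction could not be interpreted.

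If the conflict stays open, someone must choose between two definitions of a prespecified endpoint when the data are already in hand.

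**Working it through.** **1. The texts side by side**

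| Place | Qualifier *new* present? |
|---|---|
| Protocol 2.9, item 3 (list) | yes |
| Protocol 3.6.2, item 3 (definition) | yes |
| SAP 1.9, item 3 (list) | yes |
| SAP 2.2, item 3 (definition) | **no** |
| SAP 2.2, item 1 (organ support free days) | yes |
| Protocol 7.3 (data to be collected) | yes: "New renal replacement therapy over the hospitalization" |
| Protocol Appendix F, day-28 row on organ support | no |

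Among the four statements of this endpoint, only the SAP definition lacks the word. The sentence assigning zero for therapy throughout the 28 days lacks it in both documents.

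**2. The score of a chronic dialysis survivor under the literal SAP wording**

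With last-off, free days = 28 − day of last session. Session gaps of 2, 2 and 3 days are an assumption.

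- Followed to day 28: the last session falls on day 26, 27 or 28, so the score is 28 − 26 = 2 down to 28 − 28 = 0. Daily or continuous therapy gives 0.
- Therapy seen only until discharge and taken as off afterwards (assumption), with the last session 0 to 2 days before discharge: discharge on day 5 gives 23 to 25 days, day 7 gives 21 to 23, day 10 gives 18 to 20, and day 14 gives 14 to 16.
- Without last-off, counting only the 12 session days: 28 − 12 = 16.
- Death before day 28 gives zero under either wording.

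**3. Size of the dilution**

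The plan gives no sample size or power for this endpoint, so there is no figure of its own to reproduce. As a check on the method, the organ-failure-free-day table in protocol 9.2 (SD 12, two-sided 0.05, power 0.90) was recomputed with n per arm = 2·SD²·(1.960 + 1.282)²/d². The totals are 380, 674 and 1514 for differences of 4, 3 and 2 days, against the stated 382, 676 and 1516.

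Inputs for the illustration:

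- 1160 per arm (2320 randomized 1:1).
- Mean 20.6 and SD 11.9, the renal figures in protocol 9.2, used as stand-ins for patients not on chronic dialysis.
- A true difference of 2 days in those patients (assumption).
- A chronic share f of 2% to 15% (assumption), with every such patient scoring zero. This is close to the worst case for full follow-up to day 28.

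Formulas:

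- Observed difference = (1 − f)·2.
- Variance with the zeros = (1 − f)(11.9² + 20.6²) − [(1 − f)·20.6]².
- Power ≈ Φ(difference ÷ [SD·√(2/n)] − 1.96).

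For f = 10%:

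- With the zeros: variance = 0.90 × 565.97 − 18.54² = 509.37 − 343.73 = 165.64, so SD = 12.87. The difference is 1.80 and its standard error 12.87·√(2/1160) = 0.534. Then 1.80/0.534 = 3.37, and power = Φ(1.41) = 0.92.
- Patients left out: n = 1044 per arm, SD 11.9, difference 2. The standard error is 0.521, the ratio 3.84, and power 0.97.

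| Assumed share | Observed difference (days) | SD with zeros | Power with zeros | Power, patients left out |
|---|---|---|---|---|
| 2% | 1.96 | 12.13 | 0.97 | 0.98 |
| 5% | 1.90 | 12.44 | 0.96 | 0.98 |
| 10% | 1.80 | 12.87 | 0.92 | 0.97 |
| 15% | 1.70 | 13.21 | 0.87 | 0.96 |

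With a true difference of 1 day the corresponding powers are 0.45 against 0.51 at 5%, and 0.39 against 0.48 at 10%.

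**The case against.** The best defence is that the intended meaning can be recovered. SAP 1.9 and both protocol statements say new therapy, the data item in protocol 7.3 is new therapy, and SAP 2.2 rules chronic patients out of items 8 and 9. On that view this is one dropped word that a careful analyst would correct. The argument stands as far as intent goes. It does not remove the contradiction: the sentence at fault is the operational one, and the day-28 row of Appendix F does not carry the qualifier either.

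A reader might infer that every chronic dialysis patient scores exactly zero whatever the treatment does. The documents do not support that. The explicit zero rule covers therapy over the whole 28 days, which intermittent dialysis does not clearly meet. The near-zero score comes from last-off with follow-up to day 28. If therapy is observed only to discharge, the score can be far higher and would then follow length of stay.

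A reader might also infer a decisive loss of power. That depends on the dialysis share and the effect assumed. A scenario whose test statistic starts near 1.96 makes any dilution look critical. With the renal SD in protocol 9.2 and a 2-day difference, the loss at a 5% or 10% share is modest.

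Finally, leaving chronic patients out does not rescue the dialysis subgroup for this endpoint, since it would contain no data. Nor does item 8 settle the handling: not being eligible to meet an endpoint can mean counted as a non-event. That differs from ventilator free days, where patients on chronic ventilation are expressly excluded. These points stand and shape the fix.

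**Conclusion.** The inconsistency is real and should be corrected. SAP 2.2 item 3 contradicts SAP 1.9 and the protocol, and neither document says how chronic dialysis patients are scored for this endpoint. Read literally with last-off, those who survive and are followed to day 28 score about 0 to 2 days in both arms.

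The consequence is limited to one secondary endpoint and its subgroup analysis. Organ support free days keep the word *new* in the SAP, and the primary outcome does not use renal replacement. The loss of power in the illustration is about 2 percentage points at a 5% share and 5 points at 10%. These figures rest on an assumed share, an assumed 2-day effect and borrowed values for mean and SD. They show direction and rough scale and are not an estimate for this trial.

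**What to change.** Restore *new* in SAP 2.2 item 3 so that it reads as protocol 3.6.2 item 3 does. Carry the word into the zero-score sentence as well, in both documents.

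Add one sentence to both documents, fixed before outcomes are compared by arm, choosing one of two rules for patients on renal replacement therapy before the sepsis illness:

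- they are left out of this endpoint, with the number per arm reported; or
- they are counted as free of new therapy while alive, with the existing zero for death before day 28.

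Either is consistent with the protocol's wording. Leaving them out is closer to the rules for ventilator free days and the KDIGO endpoint. Counting them as free keeps all randomized patients, but these patients then inform the endpoint only through survival. If they are left out, state that the chronic dialysis interaction will not be reported for this endpoint.

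The cost is one word, in two places, and one or two sentences. The sample size is unchanged and no new data item is needed, provided chronic dialysis status is recorded at baseline, which the planned subgroup already requires.
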